11.2 Statistical analysis plan

Statistical analysis should employ the two-sided test, and $P \leq 0.05$ indicates a statistically significant difference (unless otherwise specified).

The Continuous data should be statistically described by mean, median, standard deviation, maximum value, and minimum value; the categorical data or ranked data should be statistically described by frequency.

The test should be used to compare the Continuous data between the groups, and the χ^2 test or rank sum test should be used to compare the categorical data between the groups.

Efficacy evaluation method: the evaluation of primary efficacy evaluation indicator: the overall response rate between the experimental group and the control group should be compared by the superiority test. Hypothesis test is

$$H_0: \pi_T = \pi_C, H_1: \pi_T > \pi_C$$

The 95% CI of the difference in overall response rate between the experimental group and the control group should be calculated, and the lower limit > 0 can be considered as the establishment of superiority. Meanwhile, CMH- χ^2 with central effect should be used for comparison between groups.

Safety evaluation methods: the χ^2 test/Fisher's precision probability test should be used to compare the incidence rates of all adverse events, severe adverse events and adverse reactions between the two groups, and the normal/abnormal changes in laboratory test results before and after treatment should be described.

SAS 9.2 software should be employed for statistical analysis, and the analysis process should be all programmed.

12. Quality control of the clinical trial

(1) The preparation of test vesicle packaged chemotherapeutic drugs provided by the sponsor should conform to the relevant regulations and conditions and be subject to strict quality control.

(2) In the process of clinical study, the clinical research associate assigned by the sponsor should visit the study hospital regularly and faithfully make the inspection records to ensure that the study protocol is strictly followed and all CRFs can be filled in accurately.

(3) The laboratory tests should be conducted by study sites in accordance with the standard operating procedures (SOP). The testing methods and quality control of different study sites should be unified.

(4) The clinical laboratory of the study site should carry out internal quality control according to relevant regulations and obtain the quality assessment certificate from National Center for Clinical Laboratories.

13. Case Report Form and Statistical Report

(1) The case report form (CRF) in duplicate should be filled out (with pen or water-based black pen) by the physician in charge during clinical observation and shall not be altered at will. After verification, the physician should cross out the contents to be corrected in pen, clearly write the correct data, sign and indicate the date of correction in a responsible manner. The test reports should be attached to the CRF, and the CRF should be signed by the doctor in charge, verified and signed by the principal investigator of the institution.

(2) The statistical analysis plan should be formulated by the medical statistician according to the clinical trial protocol, and the statistical analysis report should be completed by the medical statistician according to the Biostatistics Guidelines for Clinical Trials.

14. Data Collection

During the clinical trial, the investigator should archive all original data (including laboratory test reports). The study site should regularly collect the second copy of CRF that has completed the clinical trial (copy of the clinical trial participating institution) to the trial sponsor. After the sponsor collects the second copy of all

observation forms and the clinical research associate carefully reviews and confirms that the data in the CRF meet the requirements of the trial protocol, the second copy of all observation forms should be sent to the data statistics unit for processing.

15. Summary of Reports

After the end of the trial, the data statistics center should conduct data analysis in accordance with the Statistics Guidelines for Clinical Trials. The clinical trial sponsor and participating institutions should write the clinical trial summary and sub-center summary reports based on the statistical analysis reports and the guidelines for clinical trials.

16. Investigator Responsibilities

The principal investigator and participating investigators should conduct the trial according to the clinical study protocol and in accordance to the *Declaration of Helsinki*, relevant Chinese laws and regulations and current GCP guidelines.

17. Trial Funding

A separate contract is signed for the trial to state the specific funding provision.

18. Provision for Early Termination of the Clinical Trial

The trial sponsor has the right to terminate the clinical trial at any time for management or other reasons. Once the clinical trial is terminated prematurely, the sponsor must bear all costs incurred thereby.

19. Document Archival

The case report form (CRF) should be filled in with black pen in duplicate, one for the sponsor and one for the participating institution. All original data, statistical data and summary reports should be archived by the clinical trial institution for at least 5 years after the end of the trial.

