Study objective:	To evaluate the efficacy and safety of preoperative short-course radiotherapy (SCRT) combined with subsequent chemotherapy (capecitabine and oxaliplatin) and PD1 inhibitor camrelizumab in patients with locally advanced rectal cancer (LARC).
Endpoints	
Primary endpoint: Pathological complete response (pCR) rate
 
Secondary endpoint: 3-year event-free survival rate R0 resection rate 3-year Overall survival rate Surgical complication rate Safety Quality of life

Sample size:	A total of 30 patients are planned to be enrolled in this study. The specific algorithm is as follows: this study will employ the single-arm design, with pCR rate as the primary endpoint. This study will adopt PASS 15 software, use tests for one proportion, and set $\alpha=0.025$ (one side) and $\text{power}=0.80$. The pCR rate of neoadjuvant therapy for locally advanced colorectal cancer was 15% previously, which is expected to reach 40% in this study. It is expected that 24 patients will need to be enrolled. Considering the drop-out rate of 20%, a total of 30 subjects should be enrolled
Study design	Patients with locally advanced rectal cancer (T3, T4a or 4b/N+) who are to receive preoperative neoadjuvant therapy: will receive preoperative local pelvic short-course radiotherapy. Radiotherapy will employ intensity-modulated radiation therapy, with a dose of 25 Gy/5 Fractions /1 week. One week later, a 3-week regimen of CAPOX chemotherapy combined with camrelizumab will be performed for 2 cycles. One week later, radical resection of rectal carcinoma will be performed. Postoperative adjuvant chemotherapy regimen will be determined by the doctor

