Primary objective: The primary objective is to evaluate the efficacy of preoperative short-course radiotherapy combined with neoadjuvant chemotherapy and PD1 inhibitor in the treatment for locally advanced rectal cancer

Secondary objective: The secondary objective is to evaluate the safety of preoperative short-course radiotherapy combined with neoadjuvant chemotherapy and PD1 inhibitor in the treatment for locally advanced rectal cancer

Exploratory objective: To evaluate the relation of biomarkers (e.g. PD-L1 and MSI) in tumor tissues and/or blood to PD1 efficacy and pCR

3. Study Design

A prospective, single-arm, phase II clinical trial.

4. Selection and Withdrawal of Subjects

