8.2 Efficacy evaluation

Study endpoints

The primary endpoint was pathological complete response (pCR) rate, pCR was defined as the absence of viable tumour cells in the resected primary tumour specimen and all sampled regional lymph nodes (ypT0N0).

Secondary endpoints were 3-year event-free survival rate (defined as the percentage of patients without disease recurrence or progression or death due to any cause after 3-year follow-up), R0 resection rate (defined as the rate of negative margin microscopically), 3-year OS rate (defined as the percentage of patients alive after 3-year follow-up), complication rate, safety, and quality of life. Adverse events (AEs), duration of which collection was from the time the patient signed the informed consent form to 90 days after surgery, were graded according to the National Cancer Institute Common Terminology Criteria for Adverse Events, version 5.0.

Biomarker analysis

Tissue samples or paraffin sections must be provided as a patient was enrolled. Immunohistochemistry was performed to detect the expression of PD-L1 and DNA mis-match repair (MMR) proteins (MSH6, MSH2, MLH1 and PMS2). PD-L1 combined positive score (CPS) was evaluated using PD-L1 IHC 22C3 pharmDx (Agilent Technologies Inc., California, USA), defined as the number of PD-L1 positive cells (tumour cells, lymphocytes, macrophages) as a proportion of the total number of tumour cells multiplied by 100, Positive PD-L1 expression was considered when CPS was 1 or more. Comprehensive genomic profiling was conducted using targeted gene capture-based next-generation sequencing technology. Briefly, for formalin-fixed paraffin-embedded (FFPE) tissues, hematoxylin and eosin staining (H&E staining) was performed, and the stained sections were evaluated by a pathologist to ensure the tumor cells of $\geq 20\%$. DNA was extracted from the tumor tissues of patients using standard methods. A panel of 418 genes was captured and then sequenced through the Illumina NovaSeq6000 platform (Illumina, San Diego, USA) with 2×150 bp paired-end reads. The average of sequencing depth of tumor

tissues was $\geq 1000X$. Genomic alterations including tumor mutation burden (TMB), single nucleotide variants (SNV), short and long insertions and deletions (INDELs), copy number variants (CNV), and gene fusions were assessed.

Statistical analysis

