According to the previous studies, the pCR rate after preoperative CRT in patients with LARC is approximately 15%. We expected that the regimen of SCRT combined with subsequent chemotherapy and camrelizumab could increase the pCR rate from 15% to 40%. A sample size of 24 patients was required to provide at least 80% power to detect this estimated improvement, in one-sided χ^2 -test with a significance level of 2.5%, and a 20% dropout was considered, resulting in that a total sample size of 30 patients was planned for this study.

Statistical analyses were conducted using SAS® software (version 9.2, SAS Institute Inc, Cary, USA). Continuous variables were summarized using medians and ranges, and categorical variables were described using the frequency and percentage. Baseline and safety analyses were performed for all enrolled patients (intention-to-treat [ITT] population), and efficacy analyses were conducted for those who administrated at least 1 dose of camrelizumab (full analysis set [FAS] population). P value of less than 0.05 was considered statistically significant.

The exploratory objective is: to evaluate the relation of biomarkers (e.g. PD-L1 and MSI) in tumor tissues and/or blood to PD1 efficacy and pCR. Biomarker detection will be carried out with the treated tissue and/or blood obtained prior to treatment.

Continuous variables that conform to normal distribution will be expressed as mean +/- standard deviation, minimum value and maximum value, and those do not conform to normal distribution will be expressed as median; categorical variables will be described in frequency and percentage, and 95% confidence interval will be calculated if necessary. Mean values between the two groups will be compared by t test, and the rates between the two groups will be compared by chi-square test. Survival analysis will be performed by the Kaplan-Meier method. Comparison between groups will be performed by bilateral log-rank test. All tests are two-sided, and 0.05 is taken as the level of the tests.

9. Adverse Event Monitoring

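### Section 11.2 sets the primary analysis as a two-group superiority test of overall response rate, which cannot be run in a single-arm trial whose primary endpoint is pCR

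*Protocol*

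**What the plan says.** Section 3 describes the trial as "A prospective, single-arm, phase II clinical trial". The synopsis repeats this under sample size ("this study will employ the single-arm design, with pCR rate as the primary endpoint"), and section 8.2 confirms the endpoint: "The primary endpoint was pathological complete response (pCR) rate", defined there as ypT0N0.

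The sample size is a one-sample calculation. The synopsis says to "use tests for one proportion" and gives the reference: "The pCR rate of neoadjuvant therapy for locally advanced colorectal cancer was 15% previously". Section 8.2 says the regimen "could increase the pCR rate from 15% to 40" per cent, and names a one-sided chi-square test at 2.5%. It assigns efficacy analyses to patients with at least one camrelizumab dose (the full analysis set, FAS).

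Section 11.2 then describes the primary efficacy analysis differently: "the overall response rate between the experimental group and the control group should be compared by the superiority test". It gives H0: π_T = π_C against H1: π_T > π_C and a 95% confidence interval for the between-group difference, where "the lower limit > 0 can be considered as the establishment of superiority". It adds a Cochran-Mantel-Haenszel (CMH) test allowing for centre, and compares adverse events between two groups.

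Both section 8.2 (closing statistical paragraph) and section 11.2 (opening sentence) make tests two-sided at 0.05. Section 11.2 allows for exceptions that are specified elsewhere.

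**The concern.** Section 11.2 is where the protocol sets out how the primary endpoint will be tested, and what it sets out needs a second arm. No control group is defined anywhere, so π_C has no data behind it. Overall response rate is neither defined nor listed as an endpoint. Reading it as a loose rendering of pCR would not help, because the hypothesis, the interval for the difference, the CMH test and the safety comparisons would still need a control group.

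At stake is the decision rule for the primary endpoint. A reader who sets section 11.2 aside must rebuild the test from the sample-size paragraph and choose between exact and chi-square, with or without continuity correction, and between one-sided 0.025 and two-sided 0.05. With 24 to 30 patients, those choices can change the conclusion. Section 13 says the statistical analysis plan is to be drawn up from the protocol, so a plan that follows section 11.2 inherits the problem.

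**Working it through.** **1. The passages side by side**

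| Item | Synopsis, sections 3 and 8.2 | Section 11.2 |
|---|---|---|
| Arms | one | experimental and control |
| Primary measure | pCR (ypT0N0) | overall response rate |
| Reference | fixed 15% | π_C, estimated from a control group |
| Test | one proportion, one-sided 0.025 | difference of two proportions, lower 95% limit above 0; CMH by centre |
| Safety | all enrolled patients | compared between two groups |

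**2. Reproducing the planned sample size**

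Inputs from the synopsis and section 8.2: p0 = 0.15, p1 = 0.40, one-sided α = 0.025, power 0.80, dropout 20%.

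- Exact binomial, n = 24, success at 8 or more: P(X ≥ 8 | 0.15) = 0.0199 and P(X ≥ 8 | 0.40) = 0.808. Seven would give a type I error of 0.0572. No n from 15 to 23 reaches 80% power (n = 23 gives 0.763).
- Normal approximation: n' = [(1.960·√(0.15·0.85) + 0.842·√(0.40·0.60)) / 0.25]² = 19.79, so 20.
- With continuity correction: n = (n'/4)·[1 + √(1 + 2/(n'·0.25))]² = 23.62, so 24.
- Dropout: 24 / (1 − 0.20) = 30.

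The figures 24 and 30 therefore reproduce as a one-sample test. They come out under both the exact and the continuity-corrected calculation, so the sample size alone does not show which test was meant.

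**3. Could 30 patients support the section 11.2 test?**

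Assume, for contrast only, a concurrent 1:1 control at 15% against 40%. With mean rate 0.275:

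n per arm = [1.960·√(2·0.275·0.725) + 0.842·√(0.1275 + 0.24)]² / 0.25² = 48.9, so 49 per arm (98 in total; 57 per arm with continuity correction).

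Splitting 24 or 30 patients into two arms would give about 27% or 33% power. The trial was not sized for that test.

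**4. Does the choice of one-sample test matter?**

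The score statistic is z = (x − 0.15n)/√(0.1275n); the continuity correction subtracts a further 0.5 from the numerator. At n = 30, √(0.1275·30) = 1.956; at n = 24 it is 1.749. All p-values below are one-sided.

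| Result | Exact p | Lower 95% Clopper-Pearson limit | Score p | Score p, corrected |
|---|---|---|---|---|
| 8/24 | 0.0199 | 15.6% | 0.0059 (z = 4.4/1.749) | 0.013 (z = 3.9/1.749) |
| 8/30 | 0.0698 | 12.3% | 0.037 (z = 3.5/1.956) | 0.063 (z = 3.0/1.956) |
| 9/30 | 0.0278 | 14.7% | 0.0107 (z = 4.5/1.956) | 0.0204 (z = 4.0/1.956) |
| 10/30 | 0.0097 | 17.3% | 0.0025 (z = 5.5/1.956) | 0.0053 (z = 5.0/1.956) |

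At 24 patients all three tests pass 8. At 30 they part: 9 passes both chi-square versions and fails the exact test. The exact rule of 10 or more in 30 keeps power at 0.824 under 40%. A rule of 9 or more has a true type I error of 0.0278, above the planned 0.025.

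The two-sided wording is not harmless either. For 9/30, doubling the exact tail gives 2 × 0.0278 = 0.0556. Adding instead the lower-tail outcomes no more probable than 9 (only x = 0, 0.85³⁰ = 0.0076) gives 0.0354. These fall on opposite sides of 0.05.

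**The case against.** The strongest reply is that the real test is already in the protocol. Section 8.2, under its own statistical analysis subheading, names pCR, 15% against 40%, a one-sided chi-square test at 2.5%, and the FAS for efficacy. The synopsis adds that it is a test of one proportion. A null value, direction, test and level together imply a rejection rule, and section 11.2 looks like text carried over from a two-arm template. Most of this stands. A reader might infer from section 11.2 that the trial has no hypothesis for pCR and no link to 15%; section 8.2 and the synopsis show otherwise. What remains is that they give these elements to justify the sample size, while the text headed as the primary efficacy evaluation says something else.

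A reader might also infer that the above-0 criterion, applied to one arm, would let a single pCR count as success. The document does not support that. Section 11.2 applies the limit to a difference, and putting the fixed 15% in place of π_C turns it into a lower limit for pCR above 15%.

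A third reply is that the exact test is not what section 8.2 names. That is correct: adopting it raises the bar at 30 patients from 9 to 10, and the change has to be disclosed.

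**Conclusion.** Wrong as written. Section 11.2 prescribes a primary analysis that cannot be run in this trial, on a measure that is not one of its endpoints, and it contradicts the synopsis and sections 3 and 8.2. The contradiction is in the text itself and needs no outside figure.

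The practical size is one patient at the margin. With 30 analysed, 9 pCRs (30%) succeed or fail according to which one-sample test is used, exact p = 0.028 against 0.011 or 0.020. These figures assume that 15% is the fixed reference, one-sided 0.025 is the level, and all 30 enrolled patients are in the FAS; a smaller FAS has its own threshold. Because the 15%, the direction and the 2.5% level are already written down, the room for choice after the fact is limited. It is not nil, since the test and its sidedness remain open, so the test must be fixed before the data are seen.

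**What to change.** Replace the section 11.2 efficacy text with:

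> Primary analysis: pCR (ypT0N0) rate in the FAS, H0: π ≤ 0.15 against H1: π > 0.15, exact binomial test, one-sided α = 0.025. The trial succeeds if the lower limit of the two-sided 95% Clopper-Pearson interval exceeds 15%.

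Stated as a limit, the rule works for any FAS size.

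- Delete from section 11.2 the control-group hypothesis, the interval for the difference, the CMH test and the two-group safety tests. Report safety as one-group incidence with exact 95% intervals.
- State in sections 8.2 and 11.2 that the two-sided 0.05 rule does not apply to the primary test.
- Limit the two-group t-test, chi-square and log-rank wording in section 8.2 to the exploratory biomarker subgroups.
- Replace the chi-square wording in the section 8.2 sample-size text, and say that the exact test is a deliberate choice. It reproduces the planned 24 (8 or more, type I error 0.0199, power 0.808) and is stricter than the chi-square test at 30 patients. If the sponsor prefers the chi-square test, name it, state whether it is continuity-corrected, and use it throughout.

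The cost is a protocol amendment of wording only, with no added patients, visits or data. If pCR results are already known when the text is changed, date the change and report both the exact and the chi-square result.

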Discontinuation criteria:	
Trial discontinuation means the clinical trial is not completed according to protocol and is prematurely discontinued. The main purpose of trial discontinuation is to protect the rights and interests of the subjects, ensure the quality of the trial, and avoid unnecessary economic losses.
 
(1) If serious safety issues occur during the trial, the trial should be discontinued in time;
 
(2) During the trial, major errors are found in the clinical trial protocol that make evaluation of drug efficacy difficult; or major deviations from the well-designed protocol are found in the implementation that make evaluation of drug efficacy difficult if the trial is to be continued;
 
(3) The sponsor requests to discontinue the trial (because of economic or management factors or others);
 
(4) The administrative department in charge rescinds the trial.

Dose design and treatment regimen:	
Patients will receive local rectal short-course radiotherapy. Radiotherapy will employ conformal or intensity-modulated radiation therapy, with a pelvic irradiation dose of 25 Gy/5 Fractions/1 week. Then rest for 1 week after radiotherapy and begin to receive neoadjuvant chemotherapy CAPOX and PD1 inhibitor for immunotherapy, for 2 cycles. One week after the completion of neoadjuvant therapy, a second evaluation on the primary lesions will be performed, and the surgical method is total mesorectal excision. Postoperative adjuvant therapy will be started 3-4 weeks after surgery, and the treatment regimen will be determined by the investigator. The efficacy of neoadjuvant therapy on postoperative specimens will be evaluated in accordance with Rectal Cancer Regression Grade. Treatment-related toxic and side effects will be evaluated as per CTCAE 5.0 toxic and side effects evaluation criteria.

Statistical method:	
This study will employ SPSS 16.0 statistical software package for analysis. EFS and OS will be analyzed using the Kaplan-Meier method and log-rank test.

Trial schedule:	
Estimated start time of the trial: Oct. 2019
 
Estimated time of enrollment completion: Oct. 2021
 
Estimated end time of the trial: Dec. 2025

Version No.:	V2.0

Clinical Study Protocol

Version No.: V2.0

List of Abbreviations

Abbreviations and statistics descriptions (English)

dMMR	Deficient mismatch repair protein
MSI	Microsatellite instability
mCRC	Metastatic Colorectal Cancer
PD-1	Programmed cell death protein 1

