4.1 Inclusion criteria

- 1) Age 18-75 years, male or female;
- 2) Rectal cancer diagnosed by histology, with initial treatment (untreated with surgery, radiotherapy, chemotherapy or targeted therapy);
- 3) Locally advanced rectal lesion: T3, T4a or 4b/N+;

- 4) With no severe hematologic disorder, cardiac, pulmonary, hepatic or renal dysfunction, or immunodeficiency;
- 5) Hemoglobin (Hb) ≥ 9 g/dL; white blood cell (WBC) $\geq 3 \times 10^9$ /L; neutrophil (ANC) $\geq 1.5 \times 10^9$ /L; platelet (Pt) $\geq 100 \times 10^9$ /L; bilirubin < 1.5 times the upper limit of normal value; aspartate aminotransferase (AST) & alanine aminotransferase (ALT) ≤ 2.5 times the upper limit of normal value; serum creatinine ≤ 1.5 times the upper limit of normal value or creatinine clearance rate ≥ 50 mL/min; thyroid stimulating hormone (TSH) \leq ULN (If abnormal, T3 and T4 levels should be referred to simultaneously. If T3 and T4 are normal, the patient can also be enrolled);
- 6) Males or females with reproductive ability who are willing to use contraception in the trial; ECOG performance status score is 0-1;
- 7) Patients or their family members agree to participate in the study and sign the informed consent form;
- 8) No other severe cardiopulmonary diseases.

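### The one laboratory-specific summary in section 11.2 is a normal/abnormal split, so within it worsening from an abnormal baseline and the size of any change are lost

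*Protocol*

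**What the plan says.** Section 11.2, under safety evaluation methods, names one summary that is specific to laboratory results: "the normal/abnormal changes in laboratory test results before and after treatment should be described". The same sentence also covers the incidence of adverse events, severe adverse events and adverse reactions, with no breakdown by grade.

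Section 4.1, item 5, sets laboratory limits for entry that lie above the upper limit of normal:
- Liver enzymes: "aspartate aminotransferase (AST) & alanine aminotransferase (ALT) ≤ 2.5 times the upper limit of normal value".
- Kidney function: "serum creatinine ≤ 1.5 times the upper limit of normal value or creatinine clearance rate ≥ 50 mL/min".
- Thyroid: TSH should not exceed the upper limit of normal, but for an abnormal value "If T3 and T4 are normal, the patient can also be enrolled".

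The synopsis gives the same limits.

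Other places also deal with laboratory or toxicity data:
- Section 8.2 says that adverse events "were graded according to the National Cancer Institute Common Terminology Criteria for Adverse Events, version 5.0", and the synopsis says "Treatment-related toxic and side effects will be evaluated as per CTCAE 5.0 toxic and side effects evaluation criteria".
- Section 8.1 asks for changes in blood, urine and stool indexes and for liver and kidney function to be compared before and after treatment.
- Sections 7.3 and 9.1 place abnormal laboratory results under adverse event observation, with follow-up and a causality judgement.
- Section 11.2 has a general rule: "The Continuous data should be statistically described by mean, median, standard deviation, maximum value, and minimum value".

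**The concern.** A normal/abnormal classification suits a population that starts normal and a question that asks only whether a limit was crossed. Neither condition holds here. Eligibility lets patients start on the abnormal side for several tests, and the safety question concerns how bad a change is as well as whether it occurred.

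Safety is the secondary objective in section 2, and section 5.4 names the liver and the endocrine system among the organs that immune-related events can involve. With 30 planned patients, each marked laboratory change carries weight in the report. A summary that cannot show how far a patient moved from baseline gives away information that has already been collected.

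**Working it through.** The protocol reports no figure for this point, so there is nothing to reproduce. The check is whether a two-state record can distinguish the changes that matter, given the entry limits.

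**Inputs.** The summary has two states (section 11.2). AST/ALT may be up to 2.5 times the upper limit of normal (ULN) at entry (section 4.1, item 5). Classify a value as normal (N) if it is at most 1 × ULN and abnormal (A) otherwise. The post-treatment values are illustrative. The fold change is the post-treatment value divided by the baseline value.

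| Baseline (× ULN) | After treatment (× ULN) | Fold change | Cell |
|---|---|---|---|
| 0.8 | 1.0 | 1.0/0.8 = 1.25 | N to N |
| 0.8 | 2.8 | 2.8/0.8 = 3.5 | N to A |
| 0.8 | 25 | 25/0.8 = 31.25 | N to A |
| 2.5 | 1.0 | 1.0/2.5 = 0.4 | A to N |
| 2.5 | 2.8 | 2.8/2.5 = 1.12 | A to A |
| 2.5 | 4 | 4/2.5 = 1.6 | A to A |
| 2.5 | 10 | 10/2.5 = 4 | A to A |
| 2.5 | 25 | 25/2.5 = 10 | A to A |

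**What this shows.**
1. A patient who enters at 2.5 × ULN can register an improvement (A to N) but no worsening. A 12% rise and a tenfold rise share one cell.
2. A patient who enters at 0.8 × ULN registers a change when the limit is crossed, but 2.8 and 25 × ULN give the same entry.

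**Which tests.** The reasoning is the same for creatinine, which may be up to 1.5 × ULN at entry, or above that if clearance is at least 50 mL/min, and for an abnormal TSH with normal T3 and T4. The entry limit "bilirubin < 1.5 times the upper limit of normal value" also admits abnormal values, but the liver tests listed in section 7.2 are ALT and AST, so bilirubin has no scheduled repeat and is not used as an example. For haemoglobin, white cells, neutrophils and platelets the protocol gives no normal range, so whether those limits admit abnormal values is left open.

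**How many patients.** The planned total is 24/(1 − 0.20) = 30. The protocol gives no share with an abnormal baseline value. Purely for scale, an assumed share of 10% to 40% on a given test would mean 0.10 × 30 = 3 to 0.40 × 30 = 12 patients starting in the abnormal state for that test. Nothing in the protocol supports a value within that range.

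**The case against.** The best case for the plan has four parts.

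**The two-state summary is not the sole handling of laboratory data.** The continuous-data rule in the same section would show an extreme ALT as the maximum, section 8.1 compares liver and kidney function, and CTCAE 5.0 gives a graded route through adverse event reporting. This stands. A reader might infer that laboratory toxicity is analysed only as normal/abnormal, that mild and severe toxicity look alike throughout the trial report, or that severe worsening becomes invisible. The protocol does not support any of these. The loss is within one summary.

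The other provisions do not close the gap, however. A maximum shows that an extreme value occurred, but not that patient's baseline or how many patients moved that far. Section 8.1 gives no method and does not mention thyroid function. Section 11.2 does not connect laboratory results to CTCAE grade. Section 9.2 also carries a separate severity scale in which every level begins with a complaint of discomfort, so an asymptomatic laboratory change has no clear place on it.

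**Section 11.2 does not say that abnormal-to-abnormal counts as no change.** That is correct. Whatever label it is given, though, a two-state record has one cell for it, and that cell holds neither the direction nor the size of the change.

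**Table formats belong in the SAP.** Section 13 foresees a SAP, and nothing in section 11.2 forbids grade tables there, so their absence from the protocol is no fault. The point here is the method that the protocol does state. By section 13 the SAP is formulated according to the protocol, so it starts from this sentence.

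**The data are limited.** Section 7.2 schedules tests only before treatment and after the end of the trial, so a worst post-baseline value may often be the single end value. This stands, and the fix is worded accordingly.

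**Conclusion.** The point holds in a limited form. The laboratory-specific summary in section 11.2 is a weak choice for a population that may enter with abnormal AST/ALT, creatinine or TSH. Within it, worsening from an abnormal baseline cannot appear and the size of a change from normal is lost. This rests on reading the sentence as a two-state classification, which is its plain meaning, and on the entry limits in section 4.1.

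The number of patients affected cannot be derived from the protocol. The consequence is limited to secondary safety reporting and is softened by the CTCAE grading, the liver and kidney comparison and the continuous summaries. The pCR analysis, the sample size and the collection of adverse events are unaffected. It is a modest point, worth correcting because the correction is nearly free.

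**What to change.** Replace the laboratory sentence in section 11.2 with:
- for each scheduled test that has CTCAE 5.0 grades, a shift table of baseline grade against the worst available post-baseline grade;
- the number and percentage of patients who worsen by at least one grade, and who reach grade 3 or higher;
- for continuous values, a summary of within-patient change from baseline, which also serves any scheduled test without CTCAE grades.

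Stating worst available value, and naming the time points that feed it, keeps the table consistent with the schedule in section 7.2. The new sentence should refer to the CTCAE 5.0 grading in section 8.2, and the wording of sections 8.1 and 9.2 should be reconciled with it.

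The cost is one replaced sentence and a few more descriptive tables. No new data are needed, since section 7.1 records laboratory results in the CRF and section 13 attaches the test reports to it. No test is added to the schedule.
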